2.1 Primary Endpoints

2.1.1 Evaluate the change in level of self-reported financial burden from baseline (within 60 days of diagnosis) to 12 months after diagnosis of colon or rectal cancer treated with curative-intent.

2.2 Secondary Endpoints

- 2.2.1 Evaluate reported access and utilization of financial services (i.e. financial counselor, navigator, social workers) and its association to financial burden in the first 12 months after diagnosis of colon or rectal cancer treated with curative-intent.
- 2.2.2 Evaluate the change in level of self-reported financial burden and employment limitations from baseline (within 60 days of diagnosis) to 3, 6, and 12 months after diagnosis of colon or rectal cancer treated with curative-intent.
- 2.2.3 Evaluate long term outcomes at 24 months after diagnosis including financial burden, employment limitations and adherence to clinical follow-up guidelines.
- 2.2.4 Evaluate the change of quality-of-life outcome (QoL) from baseline to 12 months and its association with predictors.
- 2.2.5 Evaluate the change in level of self-reported financial burden from baseline to 12 months using alternate measures of financial burden (i.e. impact of cost questions and single item from EORTC Q30)

3. Selection of Sites

All interested NCORP sites will be invited to participate. There will be no specific exclusion criteria (i.e. minimum number of cases) because we would like to include a wide variety of different systems to better understand the variability in available financial resources and patient experiences. To ensure patient diversity in this study, all Minority/Underserved National Cancer Institute Community Oncology Research Programs (MU NCORP) sites will be specifically invited to participate.

4. Selection of Patients

Each of the criteria in the checklist that follows must be met in order for a patient to be considered eligible for this study. Use the checklist to confirm a patient's eligibility. For each patient, this checklist must be photocopied, completed and maintained in the patient's chart.

In calculating days of tests and measurements, the day a test or measurement is done is considered Day 0. Therefore, if a test is done on a Monday, the Monday four weeks later would be considered Day 28.

ECOG-ACRIN Patient No. _____

Patient's Initials (L, F, M)

NOTE: CTEP Policy does not allow for the issuance of waivers to any protocol specified criteria

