7.1.7 Study Measures and Objectives Table

Patient Questionnaires	Objectives
Baseline Questionnaire	Sociodemographics, comorbities, insurance information. Used as predictor variables for all objectives
Sociodemographic Follow-up	Sociodemographics and insurance information. Used as predictor variables for all objectives
Baseline Employment	Secondary Endpoint (2.2.2)
Follow-up Employment	Secondary Endpoint (2.2.2). Employment asked at baseline, 6, 12, and 24 months as these are time points in cancer continuum that we hypothesize change and we want to understand longitudinal change. We omitted 3 month due to patient burden. We include a 24 month time point to understand long term survivorship employment limitations.
FACT-G7	Secondary Endpoint (2.2.4). QOL asked at baseline, 6, 12, and 24 months as these are time points in cancer continuum that we hypothesize change. We omitted 3 month due to patient burden. We include a 24 month time point to understand long term survivorship QOL
Self-Efficacy	This will be used as predictor variable for all objectives. To limit burden we omitted 3 and 12 month
COST	Primary Endpoint (2.1.1)- needed at all time points to understand changes at diagnosis (baseline), beginning of tx (3), end of therapy (6), short term survivorship(12), and long term survivorship(24).
Impact of Cost	Secondary Endpoint (2.2.5)- needed at all time points to understand changes at diagnosis (baseline), beginning of tx (3), end of therapy (6), short term survivorship(12), and long term survivorship(24).
Access and Utilization of Financial Resources	Secondary Endpoint (2.2.1)- needed at all time points to understand changes at diagnosis (baseline), beginning of tx (3), end of therapy (6), short term survivorship(12), and long term survivorship(24).
Acceptability	Because of sensitive nature of questions will include these questions to assess acceptability at the 12 month time point.
Site Completed Forms	
Site Survey	Assesses available resources for financial assistance. Will be used as predictor variable
Baseline Clinical Form	Clinical information collected at all time points to correlate with primary endpoint of financial burden
Follow-up Clinical Form	Clinical information collected at all time points to correlate with primary endpoint of financial burden
24-month Follow-up Clinical Form	Clinical information and adherence variables collected for Secondary Endpoint (2.2.3)

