The principal investigators of the participating NCORP sites with CCDR components or subcomponents will be instructed to identify points-of-contact (CCDR leaders) who will be responsible for completing the site completed forms. Each participating NCORP site will complete forms including one Site Survey, Baseline Clinical form, Follow-up form at 3, 6, 12, and 24 months, and End of Study form. One Site Survey is filled out per site and should be completed within 30 days of the first participant enrollment. The Baseline, Follow-up, and End of Study form are participant-specific and contain data collection from the medical records. The designated site research coordinator will be responsible for data abstraction. Specifics about where in the medical record to locate each variable will be generally described within the form. Further questions and trouble-shooting for finding these variables will occur in personal communication with the study team.

Rev. Add1 9.2 Questionnaire Administration Process

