9.2.1 Site Survey

At the time the NCORP site opens the study, the CCDR leader will complete the "Site Survey" which asks analytic numbers for colorectal cancer at their site, resources available at their institution (i.e. social worker, financial counselor, navigator), and institutional practice regarding referrals for financial concerns. Details of where the data for of these variables can be found are included in the form. Each site with an individual CTEP ID is required to fill out one "Site Survey" within 30 days of the first participant enrollment.

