9.2.5 End of Study Clinical Form

The patient may withdraw from the study at any time for any reason. Research staff should only submit the End of Study form if the patient refuses all future direct and indirect follow-up on the study.

Study Calendar 10.

See below for a schedule of study assessments

	Baseline ¹	3 month	6 month	12 month	24 month
Patient questionnaires (min/max # questions based on skip pattern)					
Baseline Questionnaire (32/44)	Х				
Sociodemographic Follow-up (3)		Х	Х	Х	Х
Baseline Employment (18)	Х				
Follow-up Employment (14)			Х	Х	Х
FACT-G7 (7)	Х		Х	Х	Х
Self-Efficacy (6)	Х		Х	Х	
COST (11)	Х	Х	Х	Х	Х
Impact of Cost (31/41)	Х	Х	Х	Х	Х
Access and Utilization of Financial Resources (8)	Х	Х	Х	Х	Х
Acceptability (2)				Х	
Minimum/Maximum number of items at each time point	113/144	56/66	83/93	85/95	77/87
Site Completed Forms					
Site Survey ²	Х				
Baseline Clinical Form	Х				
Follow-up Clinical Form		Х	Х	Х	Х
24-month Follow-up Clinical Form					Х
End of Study Clinical Form					Х

Rev. Add1¹ Baseline study assessments must be completed within 14 days of registration. For participants who choose paper surveys, the date the survey was completed (date signed) must be within 14 days of starting radiation or chemotherapy.

² Each site with an individual CTEP ID is required to fill out one Site Survey within 30 days of the first participant enrollment.

11. Statistical Considerations

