11.4 Statistical Analysis Plan

11.4.1 Primary Objective

The primary aim is to evaluate the change in the level of self-reported financial burden from baseline (within 60 days of diagnosis) to 12 months after diagnosis of colon or rectal cancer treated with curative-intent.

We will calculate the difference of COST measurements from baseline to 12-month FU for the completers who provide data at both time points, and use the paired t-test to assess if the mean difference is significantly different from zero. In case the data are not normally distributed, nonparametric methods (e.g., Wilcoxon signed-rank test) will be used instead to assess the difference. For the participants with missing measurements at one time point, we will implement the methods as described in Section 11.4.3 to handle the missing values. The two results will be compared as a sensitivity analysis.

In addition, linear regression models with the change of COST from baseline to 12-month FU as the response variable will be fit to investigate the impact of other factors, including demographics variables (e.g., age, sex, marital status), clinical variables (e.g., stage of disease, malignancy type, chemotherapy status), baseline questionnaire variables (e.g., self-efficacy,). The three-level treatment status (IV chemotherapy, chemotherapy without IV, and no chemotherapy) will also be evaluated as a predictor. The impact of system level variables (including being designated a minority/underserved site or not, availability of financial resources for patients) will be examined in the regressions as well. Since pregnant women may have higher health-care related costs, the response will be compared between pregnant women and the others; if significant, the subset analysis may be performed in this population.

- 11.4.2 Secondary Objectives
 - 11.4.2.1 Evaluate reported access and utilization of financial services (i.e. financial counselor, navigator, social workers) and its association to financial burden in the first 12 months after diagnosis of colon or rectal cancer treated with curative-intent.

The 8-question CCVI measure as described in Section 7.1.2 will be analyzed to evaluate the change from

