To evaluate the change of financial burden from baseline to the other time points (i.e., 3-month, 6-month, and 24month), the similar approaches described for the primary objective's assessment will be implemented. In addition, longitudinal data analysis will be conducted to estimate the measurements' trajectory across all five times points. Specially, linear (or generalized linear) mixed model will be fit to study the change in the mean response over time and also the effects of cancer type, stage, treatment plan and demographics, etc. on financial burden. In case the changes in the mean response over time are not linear, the quadratic trends or non-linear trends via spline may be considered in the modeling (61). Interactions will be evaluated as well. The above analyses may be repeated to explore the categorized COST measures (63, 64).

Logistic regressions will be fit to study whether or not the level of financial burden will impact the patient's adherence to clinical follow-up guidelines, which is defined as follows: "adherent" is defined as completing all of the follow up guidelines within the 24 month study period and includes an endoscopic evaluation of their colon or barium enema, routine history and physical at least twice, and serum carcinoembryonic (CEA) level checked at least twice. The details of adherence questions can be found in Section 9.2.4.1.

11.4.2.4 Evaluate the change of quality-of-life outcome (QoL) from baseline to 12 months and its association with predictors

FACT-G7, as described in Section 7.1.4, will be analyzed to evaluate the change of QoL from baseline to 12 months. The sum of the 7-item scores will be modeled as a continuous variable in the linear regressions (57). The predictors will include demographics (age, sex, marital status), clinical variables (stage of disease, malignancy type, chemotherapy status), and financial variables (COST score). Similar to the primary aim assessment, the impact of the baseline questionnaire variables (e.g., self-efficacy) and the system level variables (including being designated a minority/underserved site or not, availability of financial resources for patients) will be examined in the models as well. FACT-G7 at 6 months will be included as an adjustment covariate. Similar analysis will be conducted to evaluate the change of FACT-G7 from baseline to 24 months as well.

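### Site-level predictors enter patient-level regressions with no stated allowance for patients sharing a site, so their standard errors are too small if changes correlate within site

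*Combined protocol and SAP*

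**What the plan says.** Section 11.4.1 fits linear regressions with each patient's 12-month change in COST as the response, and adds: "The impact of system level variables (including being designated a minority/underserved site or not, availability of financial resources for patients) will be examined". Section 11.4.2.4 models FACT-G7 in the same way, where "the system level variables (including being designated a minority/underserved site or not, availability of financial resources for patients) will be examined in the models", and extends this to a later time point: "Similar analysis will be conducted to evaluate the change of FACT-G7 from baseline to 24 months as well".

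The documents show that both variables are properties of a site:

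- **Resources.** The table in Section 7.1.7 describes the Site Survey as "Assesses available resources for financial assistance. Will be used as predictor variable". Section 9.2.1 says that it "asks analytic numbers for colorectal cancer at their site, resources available at their institution". The Study Calendar (Section 10, footnote 2) states: "Each site with an individual CTEP ID is required to fill out one Site Survey within 30 days of the first participant enrollment".
- **Designation.** Section 3 treats minority/underserved status as a property of the NCORP site: "all Minority/Underserved National Cancer Institute Community Oncology Research Programs (MU NCORP) sites will be specifically invited to participate". Section 9.1 refers to "participating NCORP sites with CCDR components or subcomponents", so a CTEP ID may sit below a parent NCORP site.

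Section 11 has one mixed model, in Section 11.4.2.3, for the COST trajectory over the five time points. It names no site term, and the two system-level variables are not among its listed effects. The sample size in Section 11.3.2 uses no ICC or design effect.

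**The concern.** When all patients at a site share a predictor's value, the information about that predictor comes largely from the number of sites. Ordinary regression counts patients as independent. Any positive within-site correlation of the outcome, with more than one patient per site, then makes the standard error too small.

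The protocol gives reason to expect site differences. Section 3 deliberately seeks varied systems and sets no minimum caseload, so unequal site sizes are likely, and unequal sizes worsen the problem.

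These are supporting analyses. They are also the only ones in Section 11 that name minority/underserved designation or site resources, and Section 1.2.5 presents the minority/underserved sites as a particular strength of the study. A chance difference between a few sites could be reported as a system effect.

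**Working it through.** **Inputs from Section 11.3.2.** SD 12 at each time, within-patient correlation 0.2, difference 2.5, two-sided 0.05, 90% power, 394 evaluable, 30% attrition, 563 enrolled. The number of sites and the ICC are not given and are assumed below.

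**The plan's own figures.** SD of change = 12 × √(2 × (1 − 0.2)) = 15.18. An exact paired t calculation gives 390. Simulating the signed-rank test at 394 (20,000 samples) gives power 0.894 against the stated 0.900. 394 / 0.70 = 562.9, so 563. These figures reproduce and do not depend on the point made here.

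**Equal sites.** With m completers per site, the design effect is DE = 1 + (m − 1) × ICC, and the true error of a nominal 5% test is 2 × (1 − Φ(1.96 / √DE)).

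| m | ICC | DE | True error | Effective N = 394/DE |
|---|---|---|---|---|
| 2 | 0.01 | 1.01 | 5.1% | 390 |
| 8 | 0.02 | 1.14 | 6.6% | 346 |
| 8 | 0.05 | 1.35 | 9.2% | 292 |
| 20 | 0.05 | 1.95 | 16.0% | 202 |

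**Which ICC matters.** It is the ICC of the change, because stable site differences cancel. If site effects at baseline and 12 months correlate s, then ICC(change) = ICC(level) × (1 − s) / (1 − 0.2). With an assumed level ICC of 0.05 and m = 8:

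| s | ICC(change) | DE | True error |
|---|---|---|---|
| 1 | 0 | 1 | 5.0% |
| 0.8 | 0.0125 | 1.0875 | 6.0% |
| 0.5 | 0.031 | 1.219 | 7.6% |
| 0.2 | 0.05 | 1.35 | 9.2% |

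**Unequal sites, by simulation.** Settings: 394 completers, SD of change 15.18, 30% of sites designated, no true effect, at least one patient per site with the rest spread by exponential weights, 4,000 runs. Each cell gives the error with no site term, then with a site random intercept and (sites − 2) degrees of freedom.

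| Sites | ICC 0 | ICC 0.01 | ICC 0.02 | ICC 0.05 |
|---|---|---|---|---|
| 150 | 4.3 / 3.8% | 5.6 / 5.0% | 5.5 / 4.8% | 6.9 / 5.4% |
| 49 | 4.7 / 3.5% | 7.1 / 5.1% | 8.2 / 5.3% | 14.3 / 6.0% |
| 20 | 5.3 / 2.8% | 8.4 / 3.9% | 13.0 / 5.7% | 22.3 / 5.9% |

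Monte Carlo error is about 0.3 points at 5%. Repeat simulations with no site term at ICC 0.05 gave 21.7% to 22.6% for 20 sites and 11.9% to 13.6% for 49, so the 49-site figure is best read as 12% to 14%. Dropping the one-patient minimum gave 8.2% for 150 sites.

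**Level of the cluster.** Take 20 equal parent sites of 3 CTEP IDs each, with designation assigned at the parent.

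| ICC, parent + CTEP ID | No site term | CTEP ID intercept | Parent intercept |
|---|---|---|---|
| 0.01 + 0.01 | 7.7% | 5.4% | 3.6% |
| 0.02 + 0.03 | 11.4% | 7.5% | 4.6% |
| 0.05 + 0 | 16.5% | 11.7% | 5.1% |

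With both predictors in one model, nested intercepts and level-specific degrees of freedom (total ICC 0 to 0.05), error was 2.4% to 5.4% for designation and 3.7% to 5.0% for resources. With no site term it reached 17.9% and 10.2%.

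**The case against.** The strongest reply is that these are exploratory predictor analyses with no hypothesis, decision rule or power of their own. The 0.05 level in Section 11.3.2 belongs to the sample-size test, so error of a 5% test is only a yardstick here. That is fair and limits the weight of the point, but too small a standard error also makes a confidence interval too narrow, whether or not anyone tests.

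Second, every size above rests on assumed inputs. Open invitation to all interested NCORP sites, with 15 to 16 accruals a month in total (Section 11.3.3), is compatible with many small sites, where the distortion is small. This stands: the documents cannot settle the size.

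Third, the ICC that counts is the residual one after demographics, stage, malignancy type, chemotherapy status and baseline measures. Case mix may explain part of any site difference, and the simulations did not include these covariates. This also stands, and it may lower the figures.

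Fourth, FACT-G7 was not quantified. Its models adjust for the 6-month score, which may absorb stable site differences, so the COST figures should not be carried over.

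Fifth, no section states that designation is assigned at a parent level; the nesting result applies only if it is.

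Finally, a plan that says linear regression does not forbid a site term. True, but nothing commits to one.

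**Conclusion.** The concern holds. Followed as written, the regressions in Sections 11.4.1 and 11.4.2.4 give standard errors that are too small for minority/underserved designation and site resources whenever changes correlate within site and sites contribute more than one patient. Under assumed site counts and ICCs, the COST error is nil at ICC 0, about 5% to 7% with many small sites (8% with very uneven ones), and material with larger sites or an ICC near 0.05: 12% to 14% with 49 unequal sites and about 22% with 20. The objections bear on size and leave the direction unchanged. The primary conclusion is not at risk; this is a worthwhile and cheap improvement to supporting analyses.

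**What to change.** Add to Sections 11.4.1 and 11.4.2.4 that every regression containing a system-level variable will include a random intercept for site, with degrees of freedom based on the number of sites, or will use site-clustered robust standard errors with a small-sample correction.

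Define site as the level at which the predictor is assigned: CTEP ID for Site Survey resources, and the parent NCORP site for designation if it is assigned there. If both are in one model, nest CTEP ID within parent and take each predictor's degrees of freedom from its own level. Do not use site fixed effects, which absorb these predictors. Report the number of sites, patients per site and the estimated ICC.

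The basic change is a sentence or two; the nested version needs slightly more, plus a check of where designation is assigned. Section 5.2 already records institution and affiliate at registration.

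The price is wider intervals for site-level effects:

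- **At true ICC 0.** The ratio of t(sites − 2) to t(392) alone widens them by 0.5% (150 sites), 2.3% (49) or 6.9% (20). Because the estimated site variance cannot be negative, mean widening in simulation was about 2%, 6% and 13%, and the test is conservative with few sites (2.6% error with 20 equal sites).
- **At ICC 0.05.** The standard error itself rises by √1.352 − 1 = 16% (49 equal sites, m = 8.04) or √1.935 − 1 = 39% (20 equal sites, m = 19.7). That increase is the correction being sought.

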1.2.6 Description of the Patient Population and Assessment Time Points in Proposed Study

This study will focus on patients receiving curative-intent treatment for colon or rectal cancer specifically for several reasons. Colon and rectal cancer were chosen because these are common malignancies that are most frequently diagnosed in the curative-intent setting (45). Because these patients typically have longer survival than those with metastatic disease, they potentially have a longer period of time to be impacted by the costs of their cancer and changes in employment. Previous studies have largely focused only on patients receiving chemotherapy and/or with metastatic disease (18, 42, 46). The recently opened SWOG trial investigating financial burden (PI: [name]) focuses on metastatic disease, and our proposed study of early stage disease will synergize with her work and will contain some common variables to allow for cross-study analysis.

There remain many unanswered questions about the financial burden that our study will address. We hypothesize that those who receive chemotherapy may have higher burden than those who do not, however this is currently unknown and will be prospectively studied in this study. We will stratify by both disease type and receipt of chemotherapy to allow for robust comparisons between these groups, which has not been previously reported in a prospective study. These comparisons may be important as we develop implementation studies and education to focus on malignancy types and treatment settings that demonstrate the highest level of burden.

We chose the time points, baseline at diagnosis, 3, 6, 12, and 24 months because they correlate with important landmarks in the treatment of colorectal cancer. At three months after diagnosis, most patients are in the initial phase of their therapy (either surgery for colon cancer or chemo-radiation for rectal). By 6 months, most patients are approaching the end of their planned therapy, and by 12 months most patients are typically done with therapy. The 24 month time point is an opportunity to collect data related to adherence to follow-up guidelines, more specifically either a colonoscopy, sigmoidoscopy, or barium enema. By analyzing data at each of these time points, there is hope to gain better understanding of the timing of changes in employment and financial burden to inform when in the cancer continuum would a future intervention be optimal.

2. Objectives

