 - 7.1.1.2 **Impact of Cost-** Patients will be asked questions about their insurance status at each assessment. They will be asked about insurance denials in addition to specific out of pocket costs related premiums, deductibles/co-pays for doctor visits, prescription and over the counter drug costs, and other services related to their cancer treatment at each time point. We will assess various lifestyle coping strategies to help pay for cancer care such as asking about cutting back on leisure activities, reducing spending on basic needs (food or utilities), spending savings, selling possessions, or borrowing money (18). We will ask questions related to communication preferences with their health care team about the cost of cancer care.
 - 7.1.2 Access and Utilization of Financial Resources- The Consumer Based Cancer Care Value Index (CCVI) was developed in collaboration with The Patient Advocate Foundation and measures

the aspects of care patients value most and the degree to which these aspects of care were experienced during their treatment. The CCCVI is a patient-centric, value-based tool that reflects the patients' vision and experience in defining the value of the care they seek. We modified items from this measure that reflect access and utilization of financial resources and experience of paying for their cancer care. This is an 8-item measure.

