baseline to 12-month FU. For the continuous item variable, we will conduct the paired t test to examine the difference if the distribution is normal. If not normally distributed, Wilcoxon signed rank test will be used. For the categorical item variable, the paired proportion test (e.g., McNemar test) will be used instead. The association between CCVI and COST measures will be evaluated using the Pearson or Spearman correlation coefficient.

Because we are aware that there is not a "gold standard" financial burden measure, we will include two other measures that have been used previously; (1) a series of items (Impact of cost questions) that are being used in the ongoing S1417CD; and (2) a single item in EORTC Q30 as our secondary endpoints. We acknowledge potential discrepancy between measures. Therefore we will conduct sensitivity analyses around the primary endpoint using the other measures and explore potential sources of discrepant outcomes.

11.4.2.2 Evaluate the change in level of self-reported financial burden and employment limitations from baseline (within 60 days of diagnosis) to 3, 6, and 12 months after diagnosis of colon or rectal cancer treated with curativeintent.

> The measurements of employment limitation by WPAI: SHP, WAI and WACS as described in Section 7.1.3 will be analyzed as continuous variables to evaluate the change from baseline to 3, 6, and 12-month FU. If the distributions are normal, we will conduct the paired t tests to examine the differences of these variables. If not normally distributed, Wilcoxon signed rank tests will be used. The association with COST measures will be evaluated using the Pearson or Spearman correlation coefficients.

11.4.2.3 Evaluate long-term outcomes at 24 months after diagnosis including financial burden, employment limitations and adherence to clinical follow-up guidelines.

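### The change analysis of financial-service use (11.4.2.1) compares only baseline with month 12, so it omits the months 3 and 6 treatment-phase visits that fall within objective 2.2.1

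*Combined protocol and SAP*

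**What the plan says.** Objective 2.2.1 (Section 2.2) asks about patients' reported access to and use of financial services and "its association to financial burden in the first 12 months after diagnosis of colon or rectal cancer treated with curative-intent". It describes a period, not a contrast between two dates.

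The study calendar (Section 10) schedules the 8-item questionnaire at baseline and at 3, 6, 12 and 24 months. The measures table (7.1.7) explains why: "Secondary Endpoint (2.2.1)- needed at all time points to understand changes at diagnosis (baseline), beginning of tx (3), end of therapy (6"), continuing to months 12 and 24.

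Section 11.4.2.1 states two analyses:

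- **Change.** The section opens with "The 8-question CCVI measure as described in Section 7.1.2 will be analyzed to evaluate the change from", and the only two visits it then names are baseline and month 12. Continuous items get a paired t test, with Wilcoxon signed-rank as the alternative for non-normal items, and a paired proportion test such as McNemar is used for categorical items.
- **Association.** "The association between CCVI and COST measures will be evaluated using the Pearson or Spearman correlation coefficient". No visit is named.

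Section 1.2.6 places month 3 in the initial phase of therapy and month 6 close to its end, and adds that "by 12 months most patients are typically done with therapy". Section 1.2.5 gives the overarching goal: to follow burden, and its interaction with service use, across the treatment schedule, so that later work can settle the timing of cost discussions.

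**The concern.** Followed as written, the change analysis uses two of the four visits inside the objective's 12-month window. The two it skips are the ones 7.1.7 ties to the start and the end of treatment. A paired comparison of the endpoints is blind to anything that rises and falls between them. If patients seek financial help mainly while on treatment, the reported result could be little or no change, or a change smaller than the one that occurred during therapy.

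Timing is at stake. The study wants to know when in the course of care burden and service use move, and this is its only stated change analysis of service use.

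**Working it through.** **Which analysis uses the month 3 and month 6 service-use data?**

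- 11.4.2.1, change: baseline and month 12 only.
- 11.4.2.1, correlation with COST: no visit stated, so months 3 and 6 are neither assigned nor excluded.
- 11.4.2.2: names 3, 6 and 12 months, but for employment limitations and their association with COST.
- 11.4.2.3: comparisons at 3, 6 and 24 months and a mixed model over all five visits, written for financial burden. The service-use measure is not mentioned.
- 11.4.2.4 and 11.4.2.5: quality of life and the alternative burden measures.

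No section assigns the month 3 and 6 responses to an analysis of change or level of service use.

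**Where the two compared visits sit.** Enrolment is before chemotherapy or radiation, or on its first day (6.3). Baseline assessments may be completed up to 14 days after registration (Section 10, footnote 1). Baseline is thus at or near the start of these treatments, and month 12 is after therapy for most patients. Section 1.2.6 counts months from diagnosis, whereas visits are counted from baseline, which may be up to 60 days later. Some month 6 visits may therefore fall after therapy has ended.

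**The plan's own figures.** None is given for objective 2.2.1. The only one borrowed here is the number of completers from 11.3.2: 394 / (1 − 0.30) = 562.9, or 563 enrolled, as stated.

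**Illustration.** The use rates are assumptions, not figures from the documents. Take a yes/no item reporting use around each visit, n = 394 paired responses, independence between visits, and a two-sided McNemar test at 0.05. With p1 and p2 the proportions at the two visits:

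- p01 = (1 − p1)·p2 and p10 = p1·(1 − p2)
- d = p01 − p10 = p2 − p1 and s = p01 + p10
- power = Φ[(|d|√n − 1.96√s) / √(s − d²)]

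Worked case, 10% to 20%: p01 = 0.18, p10 = 0.08, d = 0.10, s = 0.26. The argument is (1.985 − 0.999) / 0.500 = 1.97, so power is 0.98.

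| Assumed use at 0, 3, 6, 12 months | Planned change, 0 to 12 | Power | Change, 0 to 3 | Power |
|---|---|---|---|---|
| 10, 30, 30, 10% | 0 points | 0.05 (rejection rate) | 20 points | about 1.0 |
| 10, 30, 30, 15% | 5 points | 0.56 | 20 points | about 1.0 |
| 10, 40, 30, 20% | 10 points | 0.98 | 30 points | about 1.0 |

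Positive correlation between visits would lower s and raise power for the non-zero changes; it would not move the 0-point change. In all three patterns the planned comparison misses the peak. Only the first gives an expected change of zero.

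**The case against.** **The omission may be loose drafting.** The correlation carries no time restriction and sits under an objective covering the first 12 months, so months 3 and 6 could enter there. Nor do the plan's visit lists follow its calendar closely: 11.4.2.2 names a 3-month employment comparison, although the calendar has no employment questionnaire at month 3. This stands in part. A reader might infer that the plan discards the month 3 and 6 data altogether, and the text does not support that. The change analysis, however, is explicit about its two visits.

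**Baseline and month 12 do not bracket treatment for everyone.** Baseline may follow curative surgery or fall shortly after treatment starts. By the Table 3 thresholds, (180 + 36) / 540 = 40% of patients are in no-chemotherapy strata; the note above the table words the rectal ratio the other way, which would give (180 + 144) / 540 = 60%. Some of these patients may have completed treatment before baseline. This stands as a limit on how widely the argument applies.

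**The recall window is unknown.** Section 7.1.2 says the source instrument captures "the degree to which these aspects of care were experienced during their treatment", but the trial's items were modified and their recall period is not given. Two stronger readings are tempting. One is that baseline answers must be low by construction; that would require the modified items to keep the source wording, which is not shown. The other is that cumulative items would make the planned test uninformative; in fact the size of the change would then estimate uptake over 12 months, close to what the objective asks. If month 12 answers do look back over treatment, earlier use would be captured, but not when it occurred.

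**The consequence is limited.** This is one secondary objective in a single-arm cohort. The primary endpoint is untouched, and the timing of burden itself is analysed at all five visits.

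**Conclusion.** The point holds for the change analysis. Section 11.4.2.1 specifies baseline against month 12, while the objective covers the whole first year and 7.1.7 says the visits between are needed for it. As written, the comparison cannot show a rise and fall in service use during treatment.

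The size of the loss cannot be derived from the documents. It depends on the true pattern of use and on the items' recall window. Under assumed rates it ranges from a planned change of 0 points against 20 at month 3 to 10 points against 30. A reader might infer that the plan will wrongly report no change; that follows only if use returns to its baseline level by month 12 and the items report current use, and the documents establish neither. Loss of timing does not depend on either condition.

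This should be corrected. It affects a secondary objective and has no bearing on the primary result or the sample size.

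**What to change.** In 11.4.2.1:

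1. Analyse each CCVI item over 0, 3, 6 and 12 months with visit as a category, in a repeated-measures model suited to the item type. At minimum, make paired comparisons of baseline with each of months 3, 6 and 12, naming the visits as 11.4.2.2 does.
2. Keep baseline to month 12 as one of the reported contrasts.
3. Evaluate the CCVI-COST association at each of these visits, and say so.
4. State the recall window of the modified items, so that change between visits can be interpreted.
5. If the proportion with any use by 12 months is reported, restrict it to the yes/no use items and handle missed visits under 11.4.3. Missed visits would undercount use, and 11.3.2 assumes 30% attrition by month 12.

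**Cost:** SAP wording and a little more analysis. There are more secondary comparisons: for eight items, 8 × 3 = 24 contrasts with baseline instead of 8. All the data are already scheduled, and the sample size does not change.
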